***Do not dose patient on Baseline visit if the patient opted for LP. Refer to Visit 2.5 instead**

- Inclusion/exclusion check
- Concomitant medication reconciliation
- Labs (CBC w/ diff, CMP, TSH)
- Labs (PT, PTT, INR) to be completed and reviewed pre-lumbar puncture for all lumbar punctures
- Optical Coherence Tomography (OCT) Eye Exam (must be done before dose)
- Serum pregnancy test (if applicable)
- EKG (EKG to be completed at pre- and 6-hours post-dose \pm 10 minutes)
- Vital signs including weight
- Vital signs, post-dose, every hour for 6 hours \pm 10 minutes
- Neuro and physical exam
- Cognitive assessments for data collection only (MMSE, ADAS-cog 13, CDR, ADCS-ADL)
- Volumetric MRI (+ 4 weeks window) if vMRI was not completed during Screening
- Blood biomarkers
- Randomization*
- Dispense study drug, patient dose to be completed in-clinic*
- Drug diary provided to patient*
- Drug accountability including instructions on how to take treatment drug*
- Adverse event Assessment

The following are to be completed if participants opted into one, or both, of the optional studies:

- Lumbar puncture followed by phone check in 24hrs-48 hrs post-lumbar puncture
- Saliva collection pre- treatment dose

Visit 2.5 at Day 1 of dosing, Baseline Visit, 0.25mg/day (Only for patients who undergo LP at Baseline)

- Vital signs including weight (pre-dose), hourly vital signs \pm 10 minutes (post-dose observation for 6 hours)
- EKG (pre-dose and post-dose at 6 hours \pm 10 minutes)
- Randomization
- Dispense study drug, patient dose to be completed in-clinic
- Drug diary provided to patient
- Drug accountability including instructions on how to take treatment drug
- Adverse event assessment

Every effort will be made to complete baseline visits in the morning to allow for ample time to monitor participants after the first visit. Subjects will be administered first treatment dose in clinic and will be monitored for the following 6 hours. Every hour subjects will undergo BP/HR monitoring and AE symptom check. Investigator will be notified of BP/HR each hour with HRs rate less than 55 BPM being indicative of immediate intervention by investigator.

At the 6-hour mark after first dose participant will undergo an EKG for safety monitoring. Investigators will review EKG results for bradyarrhythmia and prolonged QT interval. Review of EKG will be completed prior to participant leaving clinic for participant safety.

Prior to leaving, patients will be given a sufficient supply of study medication (or placebo) to last until the next in-clinic visit at Visit 3 along with instructions for their use. Patients should be instructed to take their medication every morning thereafter at or around the same time.

If a titration dose is missed, or if 4 or more consecutive daily doses are missed during treatment, restart at last dose taken.

Telephone visits at Day 7,21,35,49,63,84,140,196,252, and 308 (± 7 days)

Telephone visits will be used between dose increases to monitor any safety events with participants. In addition, telephone visits will serve as safety check-in.

The following procedures will be performed at all scheduled telephone visits as shown in the schedule of events:

- Medication reconciliation
- AE assessment

Visit 3 at Day 14 (± 7 days) 0.50mg/day

The following tests and procedures will be completed in clinic:

- Concomitant medication reconciliation
- Labs (CBC w/ diff, CMP, TSH)
- EKG (pre-dose, post-dose at 6-hours ± 10 minutes)
- Vital signs including weight (pre-dose)
- Vital signs (post-dose every hour ± 10 minutes for 6 hours)
- Neuro and physical exam
- Blood biomarkers
- Dispense study drug and drug diary
- Drug accountability
- Adverse event assessment

Visit 4 at Day 28 (± 7 days) 0.75mg/day

The following tests and procedures will be completed in clinic:

- Concomitant medication reconciliation
- Labs (CBC w/ diff, CMP, TSH)
- EKG (pre-dose, post-dose at 6-hours ± 10 minutes)
- Vital signs including weight (pre-dose)
- Vital signs (post-dose every hour ± 10 minutes for 6 hours)
- Neuro and physical exam
- Blood biomarkers
- Dispense study drug and drug diary in clinic
- Drug accountability
- Adverse event assessment

Visit 5 at Day 42 (± 7 days) 1 mg/day

The following tests and procedures will be completed in clinic:

- Concomitant medication reconciliation
- Labs (CBC w/ diff, CMP, TSH)
- EKG (pre-dose, post-dose at 6-hours ± 10 minutes)
- Vital signs including weight (pre-dose)

- Vital signs (post-dose every hour \pm 10 minutes for 6 hours)
- Neuro and physical exam
- Blood biomarkers
- Dispense study drug and drug diary in clinic
- Drug accountability
- Adverse event assessment

Visit 6 at Day 56 (\pm 7 days) 1 mg/day

The following tests and procedures will be completed in clinic:

- Concomitant medication reconciliation
- Labs (CBC w/ diff, CMP, TSH)
- EKG
- Vital signs including weight
- Neuro and physical exam
- Dispense study drug and drug diary in clinic
- Drug accountability
- Adverse event assessment
- Blood biomarkers
- OCT Eye Exam

Visit 7 at Day 70 (\pm 7 days) 1mg/day

The following tests and procedures will be completed in clinic:

- Concomitant medication reconciliation
- Labs (CBC w/ diff, CMP, TSH)
- EKG
- Vital signs including weight
- Neuro and physical exam
- Blood biomarkers
- Dispense study drug and drug diary
- Drug accountability
- Adverse event assessment

Visit 8 at Day 112 (\pm 7 days) 1mg/day

The following tests and procedures will be completed in clinic:

- Concomitant medication reconciliation
- Labs (CBC w/ diff, CMP, TSH)
- EKG
- Vital signs including weight
- Neuro and physical exam
- Blood biomarkers
- Dispense study drug and drug diary
- Drug accountability
- Adverse event assessment

Visit 9 at Day 168 (\pm 7 days) 1mg/day

The following tests and procedures will be completed in clinic:

- Concomitant medication reconciliation
- Labs (CBC w/ diff, CMP, TSH)
- EKG
- OCT Eye exam
- Vital signs including weight

- Neuro and physical exam
- Blood biomarkers
- Cognitive assessments (MMSE, ADAS-Cog 13, CDR-SOB, ADCS-ADL)
- Dispense study drug and drug diary
- Drug accountability
- Volumetric MRI (+4 week window)
- Adverse event assessment

The following are to be completed if participants opted into one, or both, of the optional studies:

- *Saliva collection*

Visit 10 at Day 224 (\pm 7 days) 1mg/day

The following tests and procedures will be completed in clinic:

- Concomitant medication reconciliation
- Labs (CBC w/ diff, CMP, TSH)
- EKG
- Vital signs including weight
- Neuro and physical exam
- Blood biomarkers
- Dispense study drug and drug diary
- Drug accountability
- Adverse event assessment

Visit 11 at Day 280 (\pm 7 days) 1mg/day

The following tests and procedures will be completed in clinic:

- Concomitant medication reconciliation
- Labs (CBC w/ diff, CMP, TSH)
- EKG
- Vital signs including weight
- Neuro and physical exam
- Blood biomarkers
- Cognitive Assessments (MMSE, ADAS-Cog 13, CDR-SOB)
- Dispense study drug
- Drug accountability
- Adverse event assessment

*The following are to be completed if participants opted into one, or both, of the optional studies:
Saliva collection*

Visit 12 at Day 336 (\pm 7 days)

The following tests and procedures will be completed in clinic:

- Concomitant medication reconciliation
- Labs (CBC w/ diff, CMP, TSH)
- EKG
- Vital signs including weight
- Neuro and physical exam
- Blood biomarkers
- Dispense study drug and drug diary
- Drug accountability
- Adverse event assessment

Visit 13 at Day 364 End of Study Drug Treatment (\pm 7 days)

The following tests and procedures will be completed in clinic:

- Concomitant medication reconciliation
- Drug accountability and drug diary
- Coagulation panel labs (PT, PTT, INR) to be completed pre-optional lumbar puncture (LP).
- Labs (CBC w/ diff, CMP, TSH)
- EKG
- Vital signs including weight
- Neuro and physical exam
- Blood biomarkers
- OCT Eye Exam
- Volumetric MRI (+4 weeks)
- Cognitive Assessments (MMSE, ADAS-Cog13, CDR-SOB, ADCS-ADL)
- Drug accountability and collect drug diary
- Adverse event assessment

The following are to be completed if participants opted into one, or both, of the optional studies:

- *Lumbar puncture (to measure CSF biomarkers) followed by phone check in 24hrs post-lumbar puncture*
- *Saliva collection*

Visit 14 at Day 392 (\pm 7 days)

The following tests and procedures will be completed in clinic:

- Concomitant medication reconciliation
- Labs (CBC w/ diff, CMP, TSH)
- EKG
- Vital signs including weight
- Neuro and physical exam
- Blood biomarkers
- Adverse event assessment

The following are to be completed if participants opted for the Saliva sub-study:

- *Saliva collection*

End of Study at Day 546 (\pm 7 days)

The following tests and procedures will be completed in clinic:

- Concomitant medication reconciliation
- Labs (CBC w/ diff, CMP, TSH)
- EKG
- Vital signs including weight
- Neuro and physical exam
- Volumetric MRI (\pm 4 weeks, patients can come before or after visit for end of study)
- OCT Eye exam
- Blood biomarkers
- Cognitive assessments (MMSE, ADAS-Cog 13, CDR-SOB, ADCS-ADL)
- Adverse event assessment

The following are to be completed if participants opted Saliva sub-study:

- *Saliva collection*

Unscheduled Visits

Unscheduled visits will be at the investigator's discretion. All unscheduled visits will include the following tests and procedures:

- EKG
- Vital Signs and Weight
- Neurological and Physical Exam
- Labs (CBC with differential, CMP, TSH)
- Blood Biomarkers
- Medication reconciliation
- Adverse Event Assessment
- OCT Eye exam (in the case of blurred vision or other ocular issues)

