Objectives:	
The primary objectives are to evaluate the safety and tolerability of the drug in subjects with mild Alzheimer's disease dementia, as assessed through regular clinical evaluations throughout the dosing period. Critically, eventual treatment-emergent toxicities will drive our decision process to pursue or stop dosing. The secondary objective is to determine drug effect on relative annual brain atrophy rates in the two groups by comparing pre- and post-exposure volumetric MRI data. Tertiary objectives will be evaluated through the utilization of cognitive assessments throughout study.
 
The study design will support two exploratory objectives using blood, CSF, and saliva biospecimen collection from subjects with mild AD dementia. Blood and CSF samples will be analyzed for AD biomarkers (amyloid beta, tau, and p-tau)

	as well as CSF inflammatory markers. Saliva samples will be assessed for amyloid-beta biomarkers (primarily Aβ40 and Aβ42), which may serve as dynamic surrogate markers of therapeutic drug efficacy.
Endpoints:	
Primary Endpoint: Safety to be evaluated through reported adverse events (AEs), clinical laboratory tests (hematology, and serum chemistry,), vital signs, physical and neurological examinations, and electrocardiograms (EKGs).
 
Secondary Endpoints: Change in rates of neurodegeneration as measured with volumetric MRI.
 
Tertiary Endpoint: Cognitive changes throughout duration of the study to be evaluated through cognitive assessments, including, ADCOMS (with ADAS-Cog13, MMSE, CDR-SOB as source measures)
 
Exploratory: ADCS-ADL + CSF/blood/saliva biomarkers

Study Population:	105 male and female outpatients, 50-85 years of age, diagnosed with early/mild Alzheimer's disease dementia primarily residing in Phoenix, AZ and greater surrounding areas. Because of the local demographics, the study population will mostly consist of Caucasians, although all efforts will be made to enroll other ethnicities.

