1.1 STUDY PROCEDURES

Visit 1, Day -56 to 0 Screening Visit (Up to 8 weeks)

During the screening visit, the subject (or their legally authorized representative as appropriate) and study partner / informant (if not the same as their LAR) will sign the informed consent document prior to undergoing any study procedures.

The following tests and evaluations are used to determine subject eligibility:

- Informed consent
- Inclusion and exclusion criteria
- *CYP2C9* genotyping (buccal swab)
- Medical History & Verify Diagnosis
- Concomitant medication reconciliation
- Serum pregnancy test if applicable
- Neurological and physical examination
- Vital signs, height and weight
- Labs (CBC, CMP, Hep B, Hep C, HIV, TSH)
- Coagulation panel (PT, PTT, INR) (optional, only for patients who opt into LP/CSF substudy)
- Cognitive assessments (MMSE, Hachinski, GDS)
- Columbia Suicide Severity Rating Scale (C-SSRS)
- MRI (MRI or CT within the past 12 months of Screening Visit Day 1)
- EKG (electrocardiogram)

Patients who do not meet the eligibility criteria will not be randomized and will be considered screen failures. Screen failures may be re-screened once per PI discretion for eligibility..

If no MRI or CT scan has been completed within the past 12 months: Participants who consent will be scheduled for volumetric MRI (vMRI) to be completed prior to the Baseline Visit.

In addition, participants will be asked to complete an ophthalmic evaluation to obtain a baseline evaluation prior to the start of treatment.

Optional Lumbar Punctures for CSF Sub-Study

For lumbar punctures, the principal investigator (or sub-investigator) will perform the procedure. A separate section will be added to the consent form, which the subject (or their legally authorized representative) will sign to authorize the lumbar puncture and collection of cerebrospinal fluid (CSF). To ensure subject safety, PT, INR, and PTT levels will be checked at baseline prior to any lumbar puncture procedure and subsequently prior to each follow-up visit where a lumbar puncture is being performed.

A follow-up telephone check will be conducted the day after each lumbar puncture within 24-48 hours. If there is persistent spinal headache, a blood patch may be administered at the discretion of the investigator.

Optional Saliva Sub-Study

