Participants will have the option to provide a saliva sample via passive drooling at Baseline, Week 24, Week 52, Week 56 and Week 78. We will measure A β 40 and A β 42 in all saliva samples, as done previously³⁷.

Visit 2 at Day 1 of dosing, Baseline Visit, 0.25mg/day

Upon confirmation that all eligibility criteria have been met, baseline evaluations will be performed with subjects. These evaluations will include an assessment of concomitant therapy/medications, measurement of vital signs and body weight, collection of blood samples, vMRI (if not performed at screening) and cognitive assessments.

The following procedures and tests will be performed at baseline:

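### The baseline volumetric MRI may be taken up to 28 days after the first dose, although the plan defines the comparison as pre- versus post-exposure

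*Protocol*

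**What the plan says.** Section 1.1 heads the visit "Visit 2 at Day 1 of dosing, Baseline Visit", and the first dose is given in clinic that day unless the subject has opted for a lumbar puncture. The introductory paragraph for the visit counts volumetric MRI (vMRI) among the baseline evaluations. The procedure list then reads "Volumetric MRI (+ 4 weeks window) if vMRI was not completed during Screening". Table 1 footnote o repeats a 4-week window without giving its direction.

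Other items on the same list carry an explicit pre-dose condition: the eye examination, "Optical Coherence Tomography (OCT) Eye Exam (must be done before dose"), and the optional sample, "Saliva collection pre- treatment dose". Dosing is also held for 24 to 48 hours after a baseline lumbar puncture. Nothing equivalent is stated for vMRI.

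On screening, Section 1.1 says of subjects with no MRI or CT in the past 12 months: "Participants who consent will be scheduled for volumetric MRI (vMRI) to be completed prior to the Baseline Visit".

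The comparison itself is described as "comparing pre- and post-exposure volumetric MRI data" in the Synopsis objectives. Section 10 (Efficacy Assessments) has all 105 participants scanned at Baseline, identified as Week 0. Section 12 (General Approach) refers to volume change from pre- to post-treatment.

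**The concern.** A plus-only window on a visit that is also the first day of dosing permits the reference scan to be taken on study drug, during titration. Section 10 names neurodegeneration by vMRI as the main efficacy measure. Section 12 analyses it as change from baseline, and Section 8 also relies on vMRI to detect brain toxicity.

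A late reference is a post-randomisation, on-treatment value. Any early volume change caused by the drug, whether benefit or harm, would be partly or wholly absorbed into the reference, and only in the siponimod arm. The site would be following the protocol when it took such a scan.

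**Working it through.** **1. Direction of the window.** The protocol writes the End of Study scan with ± 4 weeks and explains that it may come before or after the visit. The Baseline, Week 24 and Week 52 scans carry a plus only. On the protocol's own notation, plus means after.

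**2. Latest permitted scan.** The visit is Day 1 and the window is 28 days, so the last permitted day is 1 + 28 = Day 29, which is 28 days after the first dose. On the nominal schedule the Day 14 titration step and the next one ("Visit 4 at Day 28") have then both passed. For lumbar puncture subjects, counting the window from Visit 2 with the first dose 1 to 2 days later, the maximum is 28 − 2 = 26 to 28 − 1 = 27 days.

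**3. Who can use the window.** It applies only when no vMRI was done at screening. Each screening rule was checked for a pre-dose vMRI requirement:

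| Rule | Subjects covered | Scan required |
|---|---|---|
| Inclusion criterion 9 | No CT or MRI in 12 months | A scan before randomisation; CT is enough |
| Section 1.1, screening | No MRI or CT in 12 months | vMRI before the Baseline visit |
| Section 10, Standard MRI | No MRI in 12 months | vMRI or CT in screening, MRI preferred |
| Table 1 footnote g | Historical CT within 12 months | Historical CT accepted |

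No rule requires a pre-dose vMRI for a subject who enters on a historical MRI. That is the clear gap. Nor is one required where a CT met the eligibility requirement.

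**4. Share of follow-up preceding the reference.**

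- Dosing period: 28/364 = 7.7% (lumbar puncture subjects: 26/364 = 7.1% to 27/364 = 7.4%).
- Time to the month-6 scan: 28/168 = 16.7% (lumbar puncture subjects: 26/168 = 15.5% to 27/168 = 16.1%).

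**5. Scan intervals, before the ±7-day visit windows.** Follow-up scans may also be 0 to 28 days late.

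| Reference scan | To Week 24 | To Week 52 |
|---|---|---|
| Day 1 | 167 to 195 days | 363 to 391 days |
| Day 29 | 139 to 167 days | 335 to 363 days |

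A scan early in screening gives longer intervals still: from Day −56 to a Week 24 scan taken 28 days late is 168 + 56 + 28 = 252 days. Unequal intervals are therefore a separate matter, which annualising by actual scan dates can handle. The problem here is the loss of an untreated reference.

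**6. Possible size of the distortion.** The protocol cites 12-month brain volume changes in secondary progressive MS of −0.28% on siponimod and −0.46% on placebo, a difference of 0.18 percentage points. If that difference accrued linearly from Day 1 (an assumption), the part falling before a Day 29 reference would be 0.18 × 28/364 ≈ 0.014 points. Under linear accrual, annualising by scan date would recover the rate. An early step change would not be recovered: it would be in the reference scan and would cancel out of the contrast.

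**7. Power.** No loss can be computed. The share of subjects affected is not stated, and Section 12 gives neither the cell means nor the within-subject correlation behind its power table.

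**The case against.** The strongest reply is that a pre-treatment scan was plainly intended. The visit text lists vMRI among the baseline evaluations, Week 0 is a nominal visit label, and a window is ordinary scheduling tolerance, probably carried over from the Week 24 and Week 52 visits. On that view this is careless wording and not a contradiction. The intention is likely, but sites follow the list, and the list permits a post-dose reference. The explicit pre-dose conditions on neighbouring items make the omission for vMRI harder to read as implied.

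Second, the affected group is narrower than all subjects. This stands. Subjects with no recent scan are directed to vMRI before Baseline in one section, and MRI is the default in another. The clear residual group is those entering on a historical MRI, and its size is not given.

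Third, the effect is small. This largely stands too. The linear illustration gives about 0.014 percentage points for a worst-case subject, the doses in that period are titration doses, and Section 12 itself says CNS effects take several weeks to become measurable. The same window applies to both blinded arms, so it would tend to dilute a true effect and would not create one under the null. That limits the severity but does not make an on-treatment scan a pre-exposure one.

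Finally, annualising by scan date can be left to the SAP. Agreed, but the timing of the scan is fixed in the protocol's visit procedures, and no SAP can supply an image that was never taken.

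**Conclusion.** The concern holds. As written, the protocol lets the reference scan for its main efficacy measure be taken as late as about Day 29, on study drug. This conflicts with its own description of the comparison in the Synopsis, Section 10 and Section 12. Per affected subject, up to 7.7% of the dosing period and 16.7% of the time to the month-6 scan can precede the reference.

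This rests on reading the plus sign as after, which the End of Study wording supports, and on the nominal visit days. The average distortion is probably modest and its total cannot be quantified, because the number of subjects without a screening vMRI is unknown. It should be fixed because the defect cannot be repaired after dosing has begun and is easily prevented.

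**What to change.** - In the Visit 2 list, state that the baseline vMRI must be completed before the first dose: at screening, at Visit 2 before dosing, or between Visits 2 and 2.5 before dosing. Remove the 4-week allowance for this scan.
- In Table 1, give the baseline vMRI its own pre-dose footnote, as the eye examination already has, so that footnote o no longer governs it.
- Align inclusion criterion 9, the Section 1.1 screening and Visit 2 text, Table 1 footnote g, and the Standard MRI paragraph in Section 10. A historical scan or a screening CT may meet eligibility but should not replace the pre-dose vMRI.
- Compute annual atrophy rates from actual scan dates, here or in the SAP.

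The cost is protocol wording and scan scheduling. The first dose may have to wait for a scanner slot. Scanning early in screening would use some slots on subjects who later fail screening; scanning at Visit 2, once eligibility is confirmed and before dosing, avoids that.

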1.2 SCHEDULE OF EVENTS (SOE)

The Schedule of Events is summarized in tabular form above and detailed below in table 1. All subjects will be expected to complete all evaluations in study.

Table 1: Study Schedule of Events

Study Visit	Screening Visit	0.25 mg/day		0.50 mg/day		0.75 mg/day		1 mg/day						
		Baseline Visit	Phone Visit	Visit 3	Phone Visit	Visit 4	Phone Visit	Visit 5	Phone Visit	Visit 6	Phone Visit	Visit 7	Phone Visit	Visit 8
Study Day (+/- 7 days)	-56 to 0	1	7	14	21	28	35	42	49	56	63	70	84	112
Study Week		0	1	2	3	4	5	6	7	8	9	10	12	16
Informed Consent	X													
Eligibility Criteria	X													
CYP2C9 genotyping	X													
Medical History	X	X	X	X	X	X	X	X	X	X	X	X	X	X
Concomitant Medications	X	X	X	X	X	X	X	X	X	X	X	X	X	X
Labs (CBC, CMP, TSH)	X	X		X		X		X		X		X		X
Coagulation panel (PT, PTT, INR)	X ^e	X ^e												
Serum Pregnancy Test	X ⁱ	X ⁱ												
EKG	X	X ^h		X ^h		X ^h		X ^h		X		X		X
Vital signs, Height/Weight	X ^k	X ^{mk}		X ^{mk}		X ^{mk}		X ^{mk}		X ^k		X ^k		X ^k
Neuro and Physical Exam	X	X		X		X		X		X		X		X
Cognitive Assessments	X ^a	X ^{b,c}												
Eye exam (OCT)		X ⁿ								X				
MRI (preferred) or CT scan ^g	X ^g													
Randomization		X												
Volumetric MRI		X ^o												
Blood biomarkers		X		X		X		X		X		X		X
(Optional) Saliva		X ^r												
(Optional) Lumbar Puncture ^d		X ^{d,e,r,s}												
Drug Accountability		X		X		X		X		X		X		X
Adverse Event Assessment		X	X	X	X	X	X	X	X	X	X	X	X	X
Dispense Study Drug and Drug Diary		X ^s		X		X		X		X		X	X	X

a. Screening MMSE, Hachinski, Geriatric Depression Scale (GDS), and CSSR-S

b. ADCOMS (MMSE, ADAS-Cog 13, CDR-SOB)

c. ADCS-ADL

d. All lumbar punctures will be followed by phone call 24-48hrs after lumbar puncture to ensure participant safety

e. Drawn only if opted in for LP. Results required before LP is completed schedule

f. Dispense of visit drug and first treatment to be completed in clinic

g. If not done within 12 months. Study willing to accept historical CT if done in past 12 months

h. EKG 6 hour post-dose observation. ±10 minutes

i. If participant is of child-bearing potential

k. Height will only be recorded at screening

m. Post-dose vitals every hour ±10 minutes

n. Eye exam (OCT) must be pre-dose

o. vMRI can be done within window of 4 weeks

p. End of study vMRI can be done within window of ±4 weeks

r. Optional substudy procedure if patient opts in

s. If patients opt in for LP on Baseline visit

do not dose until 24 to 48 hrs after LP. Follow Visit 2.5

t. Collect drug diary only on this day

Study Visit	1 mg/day										
	Phone Visit	Visit 9	Phone Visit	Visit 10	Phone Visit	Visit 11	Phone Visit	Visit 12	End of Study Drug – Visit 13	Visit 14	End of Study Visit
Study Day	140	168	196	224	252	280	308	336	364	392	546
Study Week	20	24	28	32	36	40	44	48	52	56	78
Medical History	X	X	X	X	X	X	X	X	X	X	X
Concomitant Medications	X	X	X	X	X	X	X	X	X	X	X
Labs (CBC, CMP, TSH)		X		X		X		X	X	X	X
Coagulation panel (PT, PTT, INR)									X ^e		
EKG		X		X		X		X	X	X	X
Vital Signs, Height/Weight		X ^k		X ^k		X ^k		X ^k	X ^k	X ^k	X ^k
Neuro and Physical Exam		X		X		X		X	X	X	X
Cognitive Assessments		X ^{b,c}				X ^{b,c}			X ^{b,c}		X ^{b,c}
Eye exam (OCT)		X							X		X
MRI (preferred) or CT scan											
Randomization											
Volumetric MRI		X ^o							X ^o		X ^o
Blood Biomarkers		X		X		X		X	X	X	X
(Optional) Saliva		X ^r						X ^r	X ^r	X ^r	X ^r
(Optional) Lumbar Puncture ^d									X ^{d,e,r}		
Drug Accountability		X		X		X		X	X		
Adverse Event Assessment	X	X	X	X	X	X	X	X	X	X	X
Dispense Study Drug and Drug Diary		X		X		X		X	X ^t		

a. Screening MMSE, Hachinski, Geriatric Depression Scale (GDS), and CSSR-S

b. ADCOMS (MMSE, ADAS-Cog 13, CDR-SOB)

c. ADCS-ADL

d. All lumbar punctures will be followed by phone call 24-48hrs after lumbar puncture to ensure participant safety

e. Drawn only if opted in for LP. Results required before LP is completed

schedule

f. Dispense of visit drug and first treatment to be completed in clinic

g. If not done within 12 months. Study willing to accept historical CT if done in past 12 months

h. EKG 6 hour post-dose observation. ±10 minutes

i. If participant is of child-bearing potential

k. Height will only be recorded at screening

m. Post-dose vitals every hour ±10 minutes

n. Eye exam (OCT) must be pre-dose

o. vMRI can be done within window of 4 weeks

p. End of study vMRI can be done within window of ±4 weeks

r. Optional substudy procedure if patient opts in

s. If patients opt in for LP on Baseline visit

do not dose until 24 to 48 hrs after LP. Follow Visit 2.5

t. Collect drug diary only on this day

